- 10) Hypotension based on measured resting blood pressure <90/60 at baseline; or normal resting blood pressure but evidence of orthostatic hypotension with change from supine to standing position)
- 11) Uncontrolled hypertension based on measured resting blood pressure > 180/110 at baseline
- 12) Self-reported headaches interfering with activities of daily activities more than twice a month, or use of prescription medication to prevent or treat headache in the past month (since these may be

worsened by NTG therapy)

- 13) Known allergy to nitroglycerin or other nitrate-based medications.
- 14) Known skin sensitivity to adhesives (which may generalize to the NTG patches)
- 15) Unable to complete or tolerate a brief 3-day run-in period involving the lowest available dose of NTG (0.1 mg/hr)
- 16) Currently pregnant, gave birth within the past 3 months, planning pregnancy during the study period, or unwilling to use regular barrier contraception or abstain from sexual activity to prevent pregnancy if not yet postmenopausal
- 17) Currently breastfeeding, breastfeeding within the past 3 months, or planning to breastfeed during the study period
- 18) Self-report heavy alcohol use (>3 drinks in a given day or >7 drinks per week) and uncomfortable or unwilling to decrease their alcohol intake during the study period.
- 19) Unable or unwilling to provide informed consent, fill out questionnaires, or complete study visits in English; unable or unwilling to use remote platforms (i.e., video, telephone, and/or mail-in platforms) to the above if necessary to promote social distancing
- 20) Report other conditions that, in the judgment of the investigators, render potential participants highly unlikely to follow the protocol, including plans to move, substance abuse, significant psychiatric problems, or severe dementia.

E.4 Recruitment and Consent Procedures

E.4.1 Recruitment strategies

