Study coordinators will review adherence at each scheduled follow-up visit or telephone call and address barriers to adherence in the event that participants appear to have missed days of patch use. Adherence to study medication will be assessed primarily in two ways: 1) daily study medication diaries in which participants will record their patch use and also affix their used patches to the diary, and 2) tabulation of unused medication patches at each study visit and at the study end.

F.3.1 Medication diaries

All participants who are started on study medication will be instructed to complete standardized medication diaries, in which they will record the date and time of each patch administration. Participants will also be instructed directly affix their used NTG (or placebo) patches to the appropriate section of each diary page after removing them to place a new one. Diary pages will be collected and reviewed by study coordinators at all in-person or video-based follow-up visits to promote assessment of adherence.

F.3.2 Tabulation of unused medication

Participants will be asked to return any unused medication after each in-person or video-based visit following administration of study medication; unused patches will be tabulated by study coordinators to assess adherence.

F.3.3 Adherence thresholds

The study team will monitor the proportion of participants who are using $\geq 75\%$, $50\%-74\%$, and $<50\%$ of recommended study patches over any given time interval. This will correspond roughly to participants applying/changing their patches on at least 6 days, 4-5 days, or less than 4 days per week on average.

G. STUDY MEASUREMENTS AND OUTCOMES

G.1 Study Measurements

G.1.1 Hot flash frequency and severity (before the baseline, 5-week, and 12-week clinic visits)

Change in frequency of hot flashes will be measured using a validated 7-day diary that has been widely used in prior trials of hot flash treatments, is the FDA-recommended outcome measure for studies of hormonal therapies for hot flashes, has good test-retest reliability, and is sensitive to change (Sloan, Loprinzi et al. 2001,

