Headache: Potential side effects of NTG therapy are related to the medication's vasodilatory action. The most commonly reported side effect is headache, occurring most frequently in the first 24 hours of administration (Tfelt-Hansen and Tfelt-Hansen 2009). In previous placebo-controlled trials of intermittent therapy with transdermal NTG (in which the NTG patch was removed at bedtime and replaced the next morning) at 0.2 to 0.8 mg/hr, approximately 60% of participants taking transdermal NTG reported headache, compared to 18% of participants taking placebo (Rossouw, Prentice et al. 2007). Among persons using continuous transdermal nitrate (immediately replacing the old patch with a new patch), development of tolerance to the vasodilatory effects of transdermal nitrate is expected within 12 to 24 hours, which should diminish the frequency and severity of headache. In the study team's prior pilot trial of continuous NTG for treatment of hot flashes in peri- and postmenopausal women, 37% of participants reported headache at some point during the 6-week study but the average duration of headache was less than 24 hours.

Lightheadedness/hypotension: Lightheadedness has been reported with initiation of NTG therapy, presumably due to lowering of blood pressure during the first 12 to 24 hours of administration. In prior placebo-controlled trials of intermittent NTG therapy for other indications, 6% of participants taking transdermal NTG reported transient lightheadedness thought to be associated with lowering of blood pressure, compared to 4% of participants taking placebo (Rossouw, Prentice et al. 2007). It is possible but uncommon for patients using transdermal NTG patches to develop hypotension severe enough to cause syncope. In the case of hypotension, removal of the transdermal patch should result in immediate (within seconds to minutes) normalization of blood pressure. Any lightheadedness or lowering of blood pressure associated with transdermal NTG therapy should

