Chest pain or tightness: Women reporting a history of coronary artery disease, diabetes, or two or more other major risk factors for coronary artery disease (smoking, hypertension, or hyperlipidemia with physician-recommended pharmacologic treatment) will be excluded from the study, to avoid the theoretical risk of increased chest pain or coronary events that could be associated with sustained transdermal nitrate therapy. Participants who have even one risk factor for coronary artery disease will undergo a screening ECG, and we will also exclude participants with evidence of myocardial infarction on screening ECG. Occurrence of chest pain severe enough to interfere with instrumental activities of daily living will be carefully monitored during the treatment period as part of the safety aim of the trial. Although the study team does not anticipate that many participants will develop severe chest pain interfering with daily activities, if any participant reports current or recent chest pain suggestive of ischemia at a study visit, she will be instructed to seek emergency medical attention. At the end of the treatment period, participants will be weaned off study medication rather than discontinuing medication abruptly, to minimize any risk of rebound chest pain.

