To assess tolerability and safety of NTG, we will compare group-specific rates of: 1) severe symptoms that are potentially attributable to NTG therapy (i.e., headache limiting activities of daily living, chest pain or tightness limiting activities of daily living, or syncope/fainting); and 2) any adverse events with a severity rating of 3 or higher on the CTCAE severity scale (National Cancer Institute 2009). We will also examine group-specific rates of all adverse events, regardless of severity and of anticipated relationship to NTG therapy. Inferences for rare outcomes will be obtained using Fisher's exact test. Because intention-to-treat analysis is conservative, any suggestive differences in safety outcome rates will be assessed accounting for adherence, final dose, and their interactions with treatment.

K.3 Sample Size Determination

Sample size calculations are based on parameter estimates from prior pharmacologic hot flash trials conducted by the investigators such as the FAST(Grady, Cohen et al. 2007) and CHIMES trials (Grady, Sawaya et al. 2009), which had similar eligibility criteria with respect to age, hot flashes, and treatment history. We assume the study sample will be characterized by: a) mean baseline hot flash frequency of >9 hot flashes/day; b) mean reduction in hot flash frequency in the control group of <3 hot flashes/day (i.e., <33%); c) standard deviation of change in hot flash frequency of ~4.5 hot flashes per day; and d) correlation between baseline and follow-up values of ~0.55.

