Under these assumptions, a sample size of 140 (70 per group) should provide an estimated 87% power in 2-sided tests with type-I error of 5% to detect an 20% greater reduction in hot flash frequency (or 1.8 hot flashes per day) in the active treatment arm relative to the control arm. This will correspond to a 50-55% decrease in hot flash frequency from baseline in the active treatment group, which has previously been described as a clinically important effect in prior hot flash research (Butt, Deng et al. 2007). Estimates account for correlation of the repeated measures and loss to follow-up of up to 15%, and indicate that power will remain $\geq 80\%$ even if actual effect size or other parameters are less favorable than expected. This sample of 70 per group will also provide $>80\%$ power in 2-sided tests with type-I error of 5% to detect a between-group difference in mean frequency of moderate-to-severe hot flashes of ~ 1.5 hot flashes per day, as well as ~ 3.3 points in hot flash severity scores.

K.4 Additional Statistical Considerations

K.4.1 Drop-out rates

Based on past experience, participant dropout levels are expected to remain under 15% over 12 weeks. The assumption of non-informative dropout will be examined by comparing the baseline characteristics and early post-randomization outcomes of participants who are lost to follow-up versus retained in the study. If drop-out rates differ substantially between groups, analyses will be adjusted for baseline covariates associated with retention. In sensitivity analyses, we will also use multiple imputation of missing outcomes under plausible informative missingness assumptions, along with standard methods for calculating summary estimates and confidence intervals, to assess the potential impact of loss to follow-up on treatment effect estimates (Schafer 1999).

K.4.2 Dose effects

In the event that an overall treatment benefit is detected over 12 weeks, we will conduct exploratory analyses to probe for differences in the magnitude of treatment effects by highest-achieved NTG dose, by testing for interaction between treatment assignment and highest-achieved NTG dose in a linear mixed model for change in hot flash frequency. This analysis will control for the main effect of highest achieved dose to control the placebo effect of this self-selected variable, as well as baseline factors that may confound it, such as age, body mass index, and baseline hot flash frequency or severity.

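### K.2.4 compares headache rates with no onset window and no on/off-treatment split, so an early nitroglycerin excess may be diluted and Hypothesis 4's first-24-hour prediction is not tested

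*Combined protocol and SAP*

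**What the plan says.** **Analysis.** K.2.4 states: "we will compare group-specific rates of: 1) severe symptoms that are potentially attributable to NTG therapy (i.e., headache limiting activities of daily living". The other two symptoms listed are syncope and chest pain or tightness. Adverse events of CTCAE grade 3 or higher, and all adverse events, are compared as well. Fisher's exact test is named for rare outcomes; no test is named for common ones. The section does not say whether a rate is a proportion of women or events per person-time, and it states no period.

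**Timing of the harm.** On headache, I.1.1 says: "The most commonly reported side effect is headache, occurring most frequently in the first 24 hours of administration". It expects tolerance within 12 to 24 hours of continuous use to lessen it. Hypothesis 4 in K.1 predicts more mild headache during the first 24 hours of therapy. The matching hypothesis in B.2 has no time limit. F.1.6 and H.2.5 offer dose increases at the 1-week and 2-week visits.

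**Background.** Exclusion criterion 12 in E.3 reads: "Self-reported headaches interfering with activities of daily activities more than twice a month". Women with up to two such headaches a month can therefore enter, unless they used prescription headache medication in the past month. G.1.3 and I.3.2 have coordinators ask about activity-limiting headache at every contact and record it if reported. I.3.1 counts a pre-existing condition as an adverse event only if it worsens.

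**End of collection.** H.2.5 and H.2.8 continue the same questions to a call 28 to 42 days after the 12-week visit or after stopping. I.1.2 has women weaned off study medication "to minimize any risk of rebound chest pain".

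**Data available.** Adverse event forms carry the date of onset (I.3.2). For patches, F.3.1 says of participants: "they will record the date and time of each patch administration".

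**The concern.** If the rate is taken over all follow-up, which is the natural default when no period is stated, a harm concentrated near dose starts is measured against about four months of ordinary headaches in both arms. An early excess would then look smaller than it is. Severe headache heads the list of safety outcomes in G.2, so a weak contrast there could be read as reassurance about tolerability.

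Three further gaps follow from the same silence:

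- The one time-specific safety prediction, Hypothesis 4, has no analysis.
- Events after weaning can be pooled with on-treatment events, although rebound is named as a separate risk.
- The window stays open to choice once the data are unblinded.

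The follow-up analyses that K.2.4 offers for suggestive differences use adherence and final dose, not time of onset.

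**Working it through.** **Plan's own figure.** The documents give no power, expected rate or detectable difference for headache. The 87% in K.3 concerns hot flash frequency. It reproduces approximately: with 70 × 0.85 = 59.5 women per group, a difference of 1.8, correlation 0.55 and a baseline-adjusted mean of two follow-ups (correlation between follow-ups assumed 0.55), the adjusted SD is SD × √[(1 + 0.55)/2 − 0.55²]. With SD 4.5 this is 3.09 and power is 88.8%. With SD 4.5/√[2(1 − 0.55)] = 4.74 it is 3.26 and power is 85.3%. This has no bearing on headache.

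**Observation period.** 84 + 28 = 112 days to 84 + 42 = 126 days, that is 16 to 18 weeks. The calculation uses 112.

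**Assumptions, none given in the documents.** Background activity-limiting headache is Poisson with rate λ per woman-month. NTG adds an independent acute risk q = 20%. The endpoint is at least one headache per woman, tested by Fisher's exact test, two-sided 5%, 70 per arm, with exact enumeration. The windows are 3 days after each of three dates (first randomised patch, week-1 visit, week-2 visit), 9 days in all.

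**Formulae.** Placebo: p0 = 1 − exp(−λ × days/30.4). NTG: p1 = 1 − (1 − p0)(1 − q).

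Example, λ = 0.25:
- 112 days: p0 = 1 − exp(−0.25 × 112/30.4) = 0.602 and p1 = 1 − 0.398 × 0.80 = 0.682.
- 9 days: p0 = 1 − exp(−0.25 × 9/30.4) = 0.071 and p1 = 1 − 0.929 × 0.80 = 0.257.

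**One anchor from the documents.** I.1.1 cites 18% headache on placebo in earlier trials (any headache, intermittent use). If 18% held over 112 days here, λ = −ln(0.82) × 30.4/112 = 0.054.

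The last column puts half the excess outside the windows, so q = 10% inside them.

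| λ per month | 112 days, placebo vs NTG | Power | 9 days, placebo vs NTG | Power | Windowed power, half outside |
|---|---|---|---|---|---|
| 0.02 | 7.1% vs 25.7% | 82% | 0.6% vs 20.5% | 99% | 64% |
| 0.054 | 18.0% vs 34.4% | 53% | 1.6% vs 21.3% | 97% | 55% |
| 0.1 | 30.8% vs 44.7% | 33% | 2.9% vs 22.3% | 94% | 46% |
| 0.25 | 60.2% vs 68.2% | 13% | 7.1% vs 25.7% | 82% | 31% |
| 0.5 | 84.2% vs 87.3% | 5% | 13.8% vs 31.0% | 63% | 20% |
| 1.0 | 97.5% vs 98.0% | <1% | 25.6% vs 40.5% | 40% | 12% |

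**Sensitivity.**
- With 59 per arm (15% dropout), the λ = 0.054 row becomes 45% versus 93%.
- If background varies strongly between women (gamma, shape 1), the λ = 0.25 row becomes 19% versus 82%.
- The 60% versus 18% cited in I.1.1 gives over 99% power over the whole period.
- That contrast corresponds to q = 1 − 0.40/0.82 = 51%. The same q at λ = 0.25 gives 60% versus 81% over 112 days and 70% power.

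**The case against.** Much of the case on the other side stands.

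- **Period.** K.2.4 does not state that the comparison covers 16 to 18 weeks. That is inferred from how long events are collected. The fault is an unspecified window, not a chosen one.
- **Swamping.** A reader might infer that background headache overwhelms the NTG effect. The documents do not show this. Two headaches a month is an entry ceiling, not a mean. Recent prescription headache treatment and significant run-in headache both exclude women, and the worsening rule in I.3.1 may remove usual headaches from the count. The 0.25 row implies activity-limiting headache in 60% of placebo women, whereas the only placebo figure in the documents is 18% for any headache. That figure does not prove adequate power either: it comes from intermittent use, without this run-in and over an unstated duration.
- **Timing.** A reader might infer that all NTG headache falls in the first 24 hours. I.1.1 says most frequently, and Hypothesis 4 concerns mild headache, not the activity-limiting endpoint. Every woman also meets 0.1 mg/hr NTG in the run-in, before randomisation. If half the excess lies outside the windows, the advantage nearly vanishes at λ = 0.054 (55% versus 53%) and reverses at 0.02 (64% versus 82%).
- **Titration.** A reader might infer that every woman has three dose starts. The précis calls escalation participant-directed, and women may stay on a lower dose.
- **Test.** Fisher's exact test is planned for rare outcomes only, so the power figures for common events rest on an assumption about the test.
- **Conclusion drawn.** Hypothesis 4 predicts no difference for chest pain, syncope and grade 3 or higher events, not for headache. A headache null is not a planned claim of safety.
- **Rebound.** No calculation supports a size here, and the pilot saw no chest pain on treatment or in the week after stopping.

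These points argue against replacing the overall rate. They do not supply the missing window, the missing split or the missing test of Hypothesis 4.

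**Conclusion.** The gap is real and of moderate importance. K.2.4 sets no onset window and no on/off-treatment split for symptoms collected to day 112–126, and nothing in it matches the first-24-hour prediction in Hypothesis 4. That much can be read from the text without assumptions.

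Dilution of an early excess is a possibility whose size the documents do not fix. Under an assumed 20% acute excess lying wholly inside the windows, the windowed comparison has more power in every row: 97% against 53% when the placebo proportion is 18%, and 82% against 13% at 0.25 headaches a month. The gain shrinks, and can reverse, when much of the excess falls outside the windows and background is very low. A very large excess would be found by either route at the documents' own placebo figure. The two comparisons answer different questions, early harm and 12-week tolerability, so both belong in the plan.

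**What to change.** In K.2.4:

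1. State the definition of the rate and the period for the overall comparison, and keep that comparison.
2. Beside it, pre-specify the proportion of women with a headache starting (a) in the first 24 hours after the first randomised patch and (b) within a fixed short window, for example 3 days, after the first randomised patch and after the week-1 and week-2 visit dates. Do this for activity-limiting headache, and for any headache so that Hypothesis 4 has an analysis.
3. Set the windows by visit date for every woman, whether or not she escalated, so that they do not depend on a choice made after randomisation.
4. Tabulate headache, chest pain and syncope separately for the on-treatment period and for the period from the start of weaning to the post-discontinuation call.

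The cost is SAP wording and one more table. Onset dates, visit dates and patch times are already collected. The window length is a convention and should be fixed before unblinding. No dose, schedule or clinical rule changes.

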We will conduct a randomized, double-blinded, placebo-controlled trial to evaluate the efficacy and safety of continuous transdermal NTG for treatment of hot flashes. Peri- or postmenopausal women who report frequent hot flashes, are not using other clinical hot flash treatments, have no known history of coronary disease or multiple risk factors for coronary disease, and do not have contraindications to NTG therapy will be recruited from the San Francisco Bay area. Prior to randomization, women will be asked to record all hot flashes on a validated symptom diary over a 7-day period. They will then complete a brief, 3-day run-in period in which they will wear a 0.1 mg/hr transdermal NTG patch daily to confirm willingness to apply the patch and eliminate those with sensitivities to even low-dose NTG. Women who demonstrate an average of 7 or more hot flashes per day by their screening diaries, are successful in applying a 0.1 mg/hr patch daily during the run-in period, and meet all other eligibility criteria will then be randomized in equal ratios to daily use of transdermal NTG or placebo for 12 weeks.

Randomized participants will be started on a 0.2 mg/hr NTG (or identical-appearing placebo) patch daily, as the minimum dose previously found to produce at least a one-third decrease in hot flashes in the investigators' pilot study. Women will apply a new patch each night before going to bed, immediately after removing the old patch, and avoid patch-free periods that might interfere with development of tolerance. Women will return for follow-up at 1 week, and those who show no signs of hypotension or severe hypertension and are not already completely satisfied with the change in their symptoms will be increased to a 0.4 mg/hr NTG patch (or identical-appearing placebo) daily. Based on reassessment at 2 weeks, women may increase their NTG (or placebo) patch to 0.6 mg/hr for the remaining treatment period.

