headache during the first 24 hours of therapy, but no significant differences in rates of chest pain, syncope, or severe adverse events defined by CTCAE severity grade 3 or higher.

K.2 Data Analyses

K.2.1 Analyses for Objective 1

Analyses to address aim 1 will examine change in average daily hot flash frequency from baseline to 4 and 12 weeks of treatment, measured over 7 days by validated hot flash diaries (Sloan, Loprinzi et al. 2001, Food and Drug Administration 2003). The effect of NTG therapy will be estimated using linear mixed models (LMMs) for the repeated changes, adjusting for baseline values, under the assumption of an approximately constant treatment effects at 4 and 12 weeks; in supplementary analysis we will assess evidence for differences in the treatment effects at these two time points. The distribution of the LMM residuals will be assessed using Q-Q plots, and outcomes will be transformed if necessary to achieve approximate normality. Analyses will be by intention to treat, according to treatment assignment, and without regard to adherence.

K.2.2 Analyses for Objective 2

For additional confirmation of treatment effects on frequency of any hot flashes, we will also assess treatment effects on moderate-to-severe hot flashes and on total hot flash severity scores as secondary outcomes, also assessed by diary, using the same methods. The distribution of the LMM residuals will again be assessed using Q-Q plots, and outcomes will be transformed if necessary to achieve approximate normality. Analyses will again be by intention to treat, according to treatment assignment, and without regard to adherence.

K.2.3 Analyses for Objective 3

Analyses to address aim 2 will examine changes in sleep quality and duration, anxiety and depressive symptoms, and menopausal quality-of-life from baseline to 4 and 12 weeks. These outcomes will be captured by scores on validated self-administered questionnaires, with supplementation by sleep diary in the case of sleep duration. Intervention effects on these outcomes will be estimated using LMMs, adjusted for baseline scores. Approximate normality of the residuals will be checked using Q-Q plots, and outcomes will be transformed if necessary. Analyses will once again be by intention to treat and without regard to adherence.

K.2.4 Analyses for Objective 4

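### K.2.4 tests rare harms with Fisher's exact test, which is valid but very conservative at 70 per arm; Boschloo's exact unconditional test, with its two-sided form specified, gains power within the same 5% limit

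*Combined protocol and SAP*

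**What the plan says.** K.2.4 (Analyses for Objective 4) compares the arms on severe headache, chest pain, syncope and adverse events of CTCAE grade 3 or higher, and also tabulates all adverse events. On the method it says: "Inferences for rare outcomes will be obtained using Fisher's exact test". It gives no significance level, sidedness, mid-p variant, expected event rate or power for these comparisons, and does not say whether events or women with an event are counted. It does say that suggestive differences will be examined further, allowing for adherence and final dose.

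Hypothesis 4 in K.1 (repeated in substance in B.2) predicts "no significant differences in rates of chest pain, syncope, or severe adverse events" of grade 3 or higher. The only level and power figures are for efficacy, in K.3: "a sample size of 140 (70 per group) should provide an estimated 87% power in 2-sided tests with type-I error of 5" per cent. Allocation is 1:1; eligible women "will then be randomized in equal ratios to daily use of transdermal NTG or placebo for 12 weeks".

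**The concern.** Fisher's test conditions on the total number of events. When that total is small, only a few p-values are possible, and the chance of falling at or below 0.05 under no difference can be a small fraction of 5%. K.2.4 reserves the test for exactly that situation.

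For an efficacy claim, a conservative test protects against a false claim. Here the stated hypothesis is an absence of significance, so conservatism works in favour of the predicted conclusion. An imbalance in syncope, chest pain or grade 3+ events could be reported as not significant when another exact test, with its error also held at or below 5%, would call it significant.

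**Working it through.** **The plan's own figure.** No error rate or power is stated for the safety tests, so none can be reproduced for this point. The K.3 efficacy power was checked to confirm the design inputs. These are a difference of 1.8 ("20% greater reduction in hot flash frequency (or 1.8 hot flashes per day"), an SD of 4.5 ("standard deviation of change in hot flash frequency of ~4.5 hot flashes per day"), a "correlation between baseline and follow-up values of ~0.55", and "loss to follow-up of up to 15" per cent, which leaves 70 × 0.85 = 59.5 per arm.

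- Implied SD at one visit: 4.5/√(2(1 − 0.55)) = 4.743, so the variance is 22.5.
- Baseline-adjusted variance of the mean of two follow-ups with correlation r: 22.5 × [(1 + r)/2 − 0.55²]. K.3 does not give r. With r = 0.55 this is 22.5 × 0.4725 = 10.63, an SD of 3.26.
- Power: Φ(1.8/(3.26 × √(2/59.5)) − 1.96) = Φ(1.05) = 85.3%. With r = 0.50 it is 87.2%.

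The stated 87% is reproduced to within 2 points. It does not bear on the safety tests.

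**Inputs for the safety check.** 70 per arm (K.3), with 60 per arm as a sensitivity case for 15% loss. Two-sided 5% is carried over from K.3 as an assumption. The documents give no event rates for these harms in this trial, so all rates below are assumptions.

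**Formulas.** Let x and y be the numbers of women with an event in the two arms.

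- Fisher p_F(x, y): the sum of hypergeometric probabilities, given x + y, that are no larger than that of the observed table.
- Boschloo p_B: the maximum over common rates π of Pr{p_F(X, Y) ≤ p_F(observed)}, with X and Y independent binomials.
- Size at π, or power at (π₁, π₂): the sum of b(x; n₁, π₁) b(y; n₂, π₂) over all rejecting tables. All 71 × 71 tables were enumerated.

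**True two-sided error, 70 v 70.**

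| Common rate | Fisher | Boschloo |
|---|---|---|
| 1% | 0.008% | 0.07% |
| 2% | 0.14% | 0.7% |
| 3% | 0.5% | 1.7% |
| 5% | 1.4% | 3.1% |
| 10% | 2.5% | 3.6% |
| Maximum over all rates | 3.4% | 4.9% |

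At 70 v 70, Boschloo at 5% amounts to rejecting when p_F ≤ 0.0626. Its rejection region therefore contains Fisher's, and power cannot fall.

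**Power, 70 v 70.**

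| Assumed rates | Fisher | Boschloo |
|---|---|---|
| 5% v 0% | 14% | 27% |
| 8% v 1% | 32% | 46% |
| 10% v 2% | 36% | 48% |
| 15% v 3% | 62% | 69% |
| 3% v 1% | 1.0% | 3.1% |

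**Which results change.** For five events v none, p_F = 2 × C(70,5)/C(140,5) = 2 × 12,103,014/416,965,528 = 0.058, while p_B = 0.041. Fisher needs six v none (p = 0.028). With fewer than 25 events in total, the verdicts that change at 70 v 70 are 5 v 0, 7 v 1, 9 v 2, 12 v 4 and 15 v 6.

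**Sensitivity to arm size.**

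- At 60 v 60, power for 8% v 1% goes from 23% to 36%, and for 10% v 2% from 28% to 39%.
- At 69 NTG v 71 placebo, Fisher is less conservative: its error at a 2% common rate is 0.39%, and 5 v 0 gives p = 0.027. Power for 5% v 0% goes from 26% to 46%.

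The direction of the gain is the same throughout, but its size varies.

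**The case against.** Fisher's test is valid and conventional. K.2.4 attaches no significance level to safety, promises to look further at suggestive differences, and reports group rates, so a 5 v 0 split would be seen. The DSMB also reviews unblinded safety data (I.4). The verdicts that change have Fisher p-values of only 0.055 to 0.063. All of that is correct. It means that such signals would not vanish, but it does not alter the test on which the significance wording of Hypothesis 4 turns.

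Three technical objections also stand and limit the claim.

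- **Two-sided form.** A reader might infer that any Boschloo test is never less powerful than Fisher. That holds only when the statistic is the two-sided Fisher p-value. Some software doubles a one-sided test instead: at 69 v 71, 10 v 3 events gives Fisher p = 0.044 but a doubled Boschloo p = 0.052. Table orientation matters too: scipy takes columns as arms, and a transposed 5 v 0 table returns 0.030 instead of the correct 0.041.
- **Equal arms.** The headline figures assume exactly 70 v 70. Stratified blocks of 2 and 4 (H.1.4) do not guarantee that.
- **Partial recovery.** At a 1% common rate Boschloo's own error is only 0.07%, and power for small contrasts stays very low. Another unconditional test, based on the pooled z statistic, gains more in some settings (5% v 1%: Fisher 8%, Boschloo 16%, pooled z 25%). Boschloo is therefore one defensible choice among several.

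**Conclusion.** The point holds as a recommended, inexpensive improvement. At 70 per arm Fisher's true error for harms at common rates of 2% to 10% is about 0.14% to 2.5%. Boschloo's test in the stated form adds roughly 7 to 13 percentage points of power for the four larger contrasts tabulated, with its maximum error at 4.9%. For 3% v 1% it adds about 2 points. The result rests on an assumed two-sided 5% level, assumed event rates and near-equal arms; the gain was present at 60 v 60, 69 v 71 and 68 v 72.

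Two stronger readings are not supported. The planned analysis is not invalid, because Fisher's test controls the error it claims to control. Nor would the change make a non-significant result evidence of safety: power for small differences in rare events is poor under either test, and reporting an interval for the rate difference remains a separate need.

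**What to change.** In K.2.4, replace Fisher's exact test with: *Boschloo's exact unconditional test at two-sided 5%, with the two-sided Fisher p-value as the test statistic (not a doubled one-sided test), comparing the number of randomised women with at least one event.* This also supplies the level, sidedness and counting unit that K.2.4 lacks. It should be settled before unblinding, since a choice of test made after seeing a result such as 5 v 0 would not be credible.

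The cost is one line of text, with no new data, visits or participants. The downsides are that readers know the test less well, and that the analyst must confirm that the software uses the named two-sided version and has the arms in the right orientation.
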